5.0 Study Procedures

Study population and design:

Eligible patients referred to the Division of Urology will be randomly assigned to one of the following arms: **arm A (mpMRI+ group)**, mpMRI prior to transperineal mpMRI-targeted prostate biopsy; **arm B (Standard group)**, TRUS-guided transrectal 12-core prostate biopsy.

In arm A, all patients with positive mpMRI evidence of lesions suspicious for PCa, i.e. PI RADS ≥ 3 will be submitted to transperineal MRI-targeted prostate biopsy (arm A mpMRI+). In cases of negative mpMRI results i.e. PI RADS < 3, arm A patients will

undergo TRUS-guided transrectal 12-core prostate biopsy (arm A mpMRI-)(refer to figure on page 9).

[figure not shown]
The present randomized clinical trial will compare the outcomes between the two arms.

Primary End-Points: The primary end point will be the comparison of detection rates csPCa between arm A mpMRI+ and arm B. csPCa will be defined according to the Standards of Reporting for MRI-targeted Biopsy Studies (START) criteria for targeted biopsy Gleason Score ≥ 7 or maximum cancer core length (CCL) ≥ 5 mm and the updated Epstein criteria for standard biopsy (Gleason score ≥ 7 , PSA density ≥ 0.15 , Gleason score ≥ 2 positive cores, and bilateral cancer).^{2,3} Patients will be enrolled in an intention to treat trial (See Section 9.1 Statistical Considerations).

Secondary End-Points: The secondary end points will be:

- i. Comparison of the overall detection rate of PCa and csPCa between arm A mpMRI+, arm A mpMRI-, and arm B and
- ii. Comparison of complication rates (Table 2) between arm A mpMRI+ and arm B.

If the primary end point is reached, the study will continue and remain ongoing to examine the remaining secondary end points.

Patients will be consented by Urology providers (IRB approved Co-Investigators and collaborators).

Randomization and data collection will be done by [REDACTED] [REDACTED] (study coordinator) into a REDCap generated case form (SEE APPENDIX). Study coordinator will provide de-identified data for statistical data analysis and will have master file, in password protected computer, which will link the PHI to subject ID (will be assigned by the study coordinator). After the completion of statistical analysis the master file will be deleted permanently.

Data analysis will be done by [name] (Department of Surgery analyst) supervised by [name] (PI) and statistical analysis collaborators ([name], IRB approved). Data to be analyzed will be de-identified will have no protected health information (PHI) including patient name, medical record number or date of birth.

PRE-PROCEDURE EVALUATION (within 2 months from study enrollment)

Patients are going to be evaluated at the time of office appointment by the PI and Study Collaborators

- Screening-Patients with elevated level of Prostate-specific antigen (PSA >1 ng/ml but <15 ng/ml), will be screened for research study participation by the urology providers (Co-Investigators) and [name] (PI).
- Inclusion/ Exclusion Criteria
- Consent- Patient having all the inclusion and no exclusion criteria for eligibility will be approached with research consent for participation by the urology providers (Co-Investigators) and [name] (PI).
- Demographics
- Medical History
- Surgical History
- Clinical Stage/ Digital Rectal Exam
- Vital Signs
- Physical Exam
- MRI PI-RAD Score (Grade System to classifying prostate cancer , using Pre-Procedure MRI (within 2 months from consenting & randomization))- only required for arm A
- Gland Volume (Calculated from the mpMRI and/or Ultrasound -within 2 months from consenting & randomization)
- Prostate specific antigen (PSA)

PROCEDURE EVALUATION (Surgical procedure)

Patient will undergo prostate biopsy in arm A or arm B as assigned by the randomization card

- A. Transperineal mpMRI-targeted prostate biopsy (arm A mpMRI+) (Procedure will be performed in operating room):** mpMRI-targeted prostate biopsy is standard of care and will be performed using the UroNav transperineal fusion system by a single urologist ([name]). [name] has >1 yr experience in performing mpMRI-targeted prostate biopsies. All patients will receive one dose of Ancef intravenous antibiotic at time of surgery (Vancomycin 1gm intravenous for penicillin/cephalosporin allergies or prior history of orthopedic hardware implanted within 2 years) to cover skin flora and may add additional antibiotic if prior documented UTI(s) in past then antibiotic may be tailored according to those culture(s) sensitivities) to cover enteric flora as well. All patients will receive an enema until result to be performed the morning of prostate biopsy.

The gland and the regions of interest will be contoured, and the prostate contour will be fused in real time with the TRUS image. Biopsies will be performed via a transperineal approach in the operating room. The patient will be placed in dorsal lithotomy position. mpMRI-targeted biopsies will be performed on regions of interest, and three to six cores will be obtained for biopsy from each lesion and is standard of care according to START criteria for targeted biopsy.

Multiparametric magnetic resonance imaging (mpMRI)

All of the patients in arm A will undergo mpMRI according to the European Society of Urogenital Radiology guidelines. The Prostate Imaging–Reporting and Data System (PI-RADSv2) classification (1-5) will be used to describe the lesions found: 1: very low, 2: low, 3: intermediate, 4: high, and 5: very high risk of csPCa. ⁵ The mpMRI will be performed at two centers with a 3-T scanner using a 32-channel phase array coil or four-channel phase array coil. Two experienced radiologists will analyze the mpMRI findings. Lesions with a PI-RADS score of ≥ 3 will be considered suspicious for PCa.

In cases of negative mpMRI results, arm A patients will undergo TRUS-guided transrectal 12-core prostate biopsy (arm A mpMRI–) in an identical fashion as described in arm B. Urologists (PI and Co-Investigators) will obtain SOC informed consent and perform the TRUS biopsies.

[name] will collect the biopsy sample in case of positive mpMRI results (arm A mpMRI+) and it will be sent out to pathology lab at UTMB for analysis, as SOC.

Please Note: Patients having positive mpMRI results will be referred to [name], by their primary urology (Co-Investigators and collaborators) providers, only after patients provide written consent to participation. Primary Urology (Co-Investigators and collaborators including [name]) providers will consent the patients.

- B. TRUS-guided transrectal prostate biopsy (arm B) (Procedure will be performed in Clinic):** TRUS-guided transrectal prostate biopsy will be performed using a disposable 18-gauge biopsy gun with a specimen size of 18–22 mm (Bard Medical, Covington, GA, USA) by Urology providers (Co-Investigators and [name]

(PI). All patients will receive one dose fluoroquinolone antibiotic to be taken the morning of prostate biopsy (if fluoroquinolone allergy then may substitute Bactrim DS, if prior documented UTI(s) in past then antibiotic may be tailored according to those culture(s) sensitivities) to cover enteric flora. All patients will receive an enema until result to be performed the morning of prostate biopsy.

Urologists will obtain SOC informed consent and perform the TRUS biopsies.

The 12 cores will be obtained from 12 separate anatomical regions of the prostate which is standard practice in performing TRUS-guided transrectal prostate biopsy: left medial apex, left lateral apex, left medial midgland, left lateral midgland, left medial base, left lateral base, right medial apex, right lateral apex, right medial midgland, right lateral midgland, right medial base and right lateral base.

For arm A and arm B biopsy, [REDACTED] (the study research coordinator) , [name] and [name] (Chairman, Division of Urology and study co-investigator), will monitor safety and any possible Unanticipated Adverse Device Events (UADEs). Serious Adverse Events (SAEs), Adverse Events (AEs) and UADEs assessment will be done by [name].

For Arm A and Arm B biopsy, the procedure will be performed and the sample will be sent to the Pathology lab for analysis. [name] and other urology providers will not be involved with the sample analysis and biopsy report data and results. Once the report / data is available on Epic for review, the study coordinator will extract data from patient records/ Epic into an electronic data sheet (REDCap case form, SEE APPENDIX) on which the patient will be identified by a subject ID assigned to them, no PHI information will be present. The data analysis will be performed in aggregate. A master file linking the patient to Subject ID will remain with the study coordinator for data entry purposes and once the data analysis is complete, the master file will be securely stored and password protected.

- Adverse event assessment (Tables 2 and 3)

POST-PROCEDURE EVALUATION/ END OF STUDY- (Follow-up can be done by telephone or clinical visit)

- Diagnosis of csPCa- Based on the biopsy report will be available 2-4 weeks post-procedure
- Gleason score ((Grade System to classifying PCa)- Based on the biopsy report will be available 2-4 weeks post-procedure
- Total cancer core length (mm)- Based on the biopsy report will be available 2-4 weeks post-procedure
- Maximum cancer core length (mm)- Based on the biopsy report will be available 2-4 weeks post-procedure
- Adverse event assessment- Can be done by telephone or clinical visit, usually 2-4 weeks post biopsy procedure

Table 2. Schedule of Events

Variables (Both Arm A and Arm B)	Pre-Study (within 2 months from consent and randomization)	Biopsy	Post-Biopsy Follow-up/Study End (within 2-4 wks from biopsy) Follow-up can be done by telephone or clinical visit)
Informed consent*	X		
Demographics	X		
Medical History	X		
Surgical History	X		
Clinical Stage/digital rectal exam	X		
Vital signs	X		
Height	X		
Weight	X		
PSA	X		
MRI PI-RADS (Arm A)	X	X	
Gland volume (MRI- Arm A or US- Arm B)	X	X	
Diagnosis of Prostate Cancer			X
Serum creatinine***	X		
Diagnosis of Clinically Significant Prostate Cancer**			X
Gleason score			X
Total cancer core length (mm)			X
Maximum cancer core length (mm)			X
UADE*		X	X

* Indicates study-only activity.

All other procedures/tasks are standard of care. Prostate specific antigen (PSA), Digital rectal examination (DRE), Prostate Imaging Reporting and Data System (PI-RADS), transrectal ultrasound (TRUS), Unanticipated Adverse Device Event

**Clinically significant PCa defined as targeted biopsy Gleason Score \geq or maximum CCL \geq 5 mm and the updated Epstein criteria for SB.

*** The serum creatinine assessment will be performed no more than one month prior to randomization.

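### The primary comparison uses a label, arm A mpMRI+, that means the whole randomised arm in some places and only PI-RADS ≥ 3 men in others, while Aim 1 is declared intention-to-treat

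*Combined protocol and SAP*

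**What the plan says.** The primary endpoint in Section 5.0 reads: "The primary end point will be the comparison of detection rates csPCa between arm A mpMRI+ and arm B". Section 2.0 words the endpoint and Specific Aim 1 with the same label.

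**Uses that point to the whole arm.** Section 4.0 attaches arm A mpMRI+ to the pathway men are randomised to. Section 5.0 opens by calling the randomised group "arm A (mpMRI+ group" (the closing bracket follows in the text) and later says: "The present randomized clinical trial will compare the outcomes between the two arms". The primary endpoint paragraph calls the trial intention-to-treat and refers to Section 9.0. Section 9.0 makes intention-to-treat the main analysis for Aim 1, sizes it per arm, and treats non-intention-to-treat analyses under Aim 2 as sensitivity analyses.

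**Uses that point to the subset.** Section 5.0 also says "In arm A, all patients with positive mpMRI evidence of lesions suspicious for PCa, i.e. PI RADS ≥ 3 will be submitted to" transperineal targeted biopsy and labels those men arm A mpMRI+. Men with PI-RADS below 3 become arm A mpMRI-, biopsied "in an identical fashion as described in arm B". The mpMRI paragraphs repeat the restriction: "will collect the biopsy sample in case of positive mpMRI results (arm A mpMRI" (the plus sign follows in the text). The first secondary endpoint treats the two as separate groups: "Comparison of the overall detection rate of PCa and csPCa between arm A mpMRI+, arm A mpMRI-, and arm B".

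**The concern.** The two meanings give two different primary analyses.

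PI-RADS is required only in arm A. If the label means PI-RADS ≥ 3 men, arm A loses its low-yield men (4% csPCa by Section 9.0's assumption) and arm B loses no counterparts. That comparison is neither intention-to-treat nor randomised, and it favours UroNav.

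If the label means the whole arm, the comparison is between randomised groups. The question is then whether the 30-point effect used for sizing is a whole-arm effect. Section 9.0's own figures suggest that it is not.

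The trial is un-blinded, so the group that carries the primary test should be stated beyond doubt before results are seen. The second secondary endpoint ("Comparison of complication rates (Table 2) between arm A mpMRI+ and arm B") and Aim 3 use the same label.

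**Working it through.** **Inputs.** From Section 9.0: control rate 18.1%; absolute increase 30 points; one-sided 0.05; power 80%; 31 per arm for Aim 1; 25% of arm A MRI-, with csPCa 4% in MRI- and 48% in MRI+; 72 men (36 per arm) before 10% loss, 80 in total; two-sided exact tests for analysis. From Section 1.0: 43.9% against 18.1% in the cited trial.

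**1. The plan's own figure.** With p1 = 0.181, p2 = 0.481 and mean p = 0.331, the pooled two-proportion formula gives

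n = [1.645 × √(2 × 0.331 × 0.669) + 0.842 × √(0.181 × 0.819 + 0.481 × 0.519)]² / 0.30² = 29.4, so 30 per arm.

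The plan has 31 per arm, so its figure reproduces to within one man per arm. The total also reproduces: 72 / 0.90 = 80.

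**2. Which group does 48.1% describe?**
- Aim 1 target: 18.1% + 30 = 48.1%. Section 9.0's MRI+ rate is 48%.
- Whole arm A on the same inputs: 0.75 × 48% + 0.25 × 4% = 37.0%, a gain of 37.0 − 18.1 = 18.9 points.
- MRI+ rate needed for a whole-arm 48.1%: (0.481 − 0.25 × 0.04) / 0.75 = 62.8%, against the 48% stated.

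**3. Subset reading: effect on the estimate.** The subset shows 48% where the whole arm shows 37.0%, so the apparent gain rises by 11.0 points. For an assumed MRI- share of 15% to 40%, the whole-arm rate is 41.4% to 30.4% and the added gain is 6.6 to 17.6 points.

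**4. Subset reading: effect on false positives.** Suppose the whole arm A pathway detects exactly 18.1%. The subset rate is then (0.181 − 0.25 × 0.04) / 0.75 = 22.8%. With 27 subset men (0.75 × 36) against 36 in arm B, I summed the exact binomial probabilities of all outcomes that two-sided Fisher rejects at 5%:

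| True rates (subset vs arm B) | Rejections favouring UroNav | All rejections |
|---|---|---|
| 18.1% vs 18.1% | 1.8% | 3.2% |
| 22.8% vs 18.1% | 5.2% | 5.7% |

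The 5.2% becomes 3.3% to 10.8% for an MRI- share of 15% to 40%, and 6.7% to 3.0% for an MRI- csPCa rate of 0% to 12% (both ranges assumed).

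**5. Whole-arm reading: power at 36 per arm against 18.1%, by exact enumeration.**

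| Whole-arm A rate | Gain | One-sided z (as sized) | Two-sided Fisher (as analysed) |
|---|---|---|---|
| 48.1% (plan's target) | 30.0 points | 87% | 71% |
| 43.9% (Section 1.0, if a whole-arm rate) | 25.8 points | 78% | 58% |
| 37.0% (Section 9.0 inputs) | 18.9 points | 56% | 34% |

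The gap between the two power columns comes from sizing one-sided and testing two-sided. That is a separate issue; the comparison that matters here runs down each column.

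**The case against.** The strongest reply is that the plan already chooses the whole arm. The endpoint paragraph calls the trial intention-to-treat and sends the reader to Section 9.0, which makes that the main analysis for Aim 1, sizes it per arm and ranks non-intention-to-treat work as sensitivity analysis. On this view the label is loose drafting. Much of this stands: the whole arm is the better-supported reading, and the ranking limits the room to choose a population after results are known. It does not close the matter. Section 9.0 never says that Aim 1 includes the mpMRI- men, and the endpoint keeps the label that Section 5.0 gives to PI-RADS ≥ 3 men and sets apart from mpMRI-. The design figure cited in Sections 2.0 and 5.0 might settle it, but it is not available in the text reviewed.

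A second reply is that 30 points is simply an effect to detect, and that the 25%, 4% and 48% inputs are given for Aim 2. That is fair as far as it goes, since no text says how the 30 points were derived. The inputs also fit poorly with the 43.9% attributed to the same cited trial: with 25% MRI- at 4%, a whole-arm 43.9% needs (0.439 − 0.01) / 0.75 = 57.2% in MRI+ men. So 37.0% is one scenario, and a range is needed.

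A third reply is that the planned Fisher test is conservative, so the decision-level harm is small. This stands for the base case. The 11-point shift in the estimate and the loss of randomised groups remain.

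**Conclusion.** The label conflict is real and affects the primary analysis, so it must be corrected. Read literally, the endpoint sets a post-randomisation subset of arm A against all of arm B and overstates UroNav's gain by about 11 points on Section 9.0's rates (6.6 to 17.6 over the assumed MRI- shares). Read as intention-to-treat, the groups are randomised, but the 30-point effect is not supported by Section 9.0's inputs. At 36 per arm, power is about 56% to 78% by one-sided z, or 34% to 58% by two-sided Fisher, over whole-arm rates of 37.0% to 43.9%.

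Four stronger readings are tempting, and the documents do not support them:
- **That the sponsor plans a subset analysis.** The intention-to-treat statements point the other way.
- **That the sample size was built on the subset rate.** The match of 48.1% with 48% suggests this, but nothing states it.
- **That the subset test has gross type I error.** Under two-sided Fisher, total rejections move only from 3.2% to 5.7% in the base case.
- **That a whole-arm comparison settles everything.** Sections 2.0 and 5.0 define csPCa differently for targeted and standard biopsy, so the outcome would still not be common to both arms. That is a separate issue.

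**What to change.** 1. In Section 2.0 (endpoint and Aim 1) and Section 5.0, define the primary comparison as csPCa detection in all men randomised to arm A, mpMRI+ and mpMRI- combined, against all men randomised to arm B.
2. Reserve arm A mpMRI+ for PI-RADS ≥ 3 men, and correct Section 4.0 and the opening of Section 5.0 to say arm A.
3. Label any comparison of mpMRI+ or mpMRI- men with arm B as a non-randomised secondary analysis.
4. In Section 9.0, restate the whole-arm effect (18.9 to 25.8 points) and the power it gives with 36 evaluable men per arm, as a range over whole-arm rates of 37.0% to 43.9%.

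The cost is wording in Sections 2.0, 4.0 and 5.0 and one revised power paragraph. Enrolment does not change, and the primary endpoint needs no extra biopsies because mpMRI- men are already biopsied under the plan. The downside is that the stated effect and power become less favourable, and the sponsor would have to accept that openly.

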4.0 Treatment Assignment/Randomization

Enrollment into the study is defined as following randomization. Patients who fulfill all eligibility criteria and have provided written consent will be randomized to undergo mpMRI followed by targeted biopsies (arm A mpMRI+) or TRUS transrectal biopsy (arm-B) by the PI and authorized study collaborators. [REDACTED], study coordinator, will have access to randomization, generated by an electronic randomization system provided by REDCap.

Sequence generation

Patients will be randomly assigned to arm A or arm B following a 1:1 simple randomization procedure according to a computer-generated randomization list provided by REDCap. [REDACTED] [REDACTED] study coordinator, and a designated back-up will be the only persons to have access of the REDCap randomization list.

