9.0 Statistical Considerations

This is an un-blinded, single center, randomized controlled trial. The associations between categorical variables and the arms will be analyzed with Fisher's exact test; Mann-Whitney and Kruskal-Wallis tests for continuous variables. p values will be obtained by the two-sided exact method at the conventional 5% significance level. Using an intention to treatment power analysis for Aim 1, a sample size of 62 patients (31 per arm) will be required to detect a 30% absolute increase in the detection rate of csPCa, with a one-sided 0.05 significant level, a type II error of 0.20, and the rate of csPCa being 18.1% from standard biopsy,⁷ based on two-sample test for proportions. For Aim 2, assuming about 25% of Arm A is MRI- and rate of csPCa was 4% in MRI- and 48% in MRI+ (based on the results from paper published by Porpiglia et al⁷) and using one-way ANOVA test, it will require 72 patients (36 per arm) to detect this difference with power of 80%. Considering 10% of patients will be lost to follow-up, the total sample size needed will be 80 patients. No interim analyses will be planned, and all procedures will be performed on an intention-to-treat basis for Aim 1 as our main analyses. Non-intent to treat analyses under Aim 2 will be treated as sensitivity analyses. All analyses will be performed with SAS version 9.4 (SAS Institute, Cary, NC).

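### No masking of the pathologist is described and the coordinator who records csPCa knows the arm, so unmasked reading could bias the primary comparison

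*Combined protocol and SAP*

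**What the plan says.** Section 9.0 states: "This is an un-blinded, single center, randomized controlled trial". No section names a masked assessor, a second or central reading, or adjudication of csPCa.

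Section 5.0 makes one separation. For both arms, "the procedure will be performed and the sample will be sent to the Pathology lab for analysis", and the operators and "other urology providers will not be involved with the sample analysis and biopsy report data and results". For MRI-positive men in arm A, the sample is handled routinely: "it will be sent out to pathology lab at UTMB for analysis, as SOC".

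The outcome is recorded by the study coordinator. Once the report is in the hospital record, "the study coordinator will extract data from patient records/ Epic into an electronic data sheet". Under section 4.0, the "study coordinator, and a designated back-up will be the only persons to have access of the REDCap randomization list". Section 5.0 gives randomization and data collection to this same role, which also keeps the file linking patient to subject ID.

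The post-procedure list in section 5.0 contains "Diagnosis of csPCa- Based on the biopsy report will be available 2-4 weeks post-procedure". Gleason score, total core length and maximum core length are separate items there and in Table 2.

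Sections 2.0 and 5.0 define csPCa for targeted biopsy by Gleason score of at least 7 or maximum core length of at least 5 mm. Standard biopsy has a different, multi-item rule based on the updated Epstein criteria.

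**The concern.** Gleason 6 against 7, and a core length just under or over 5 mm, are readings that involve judgement. A reader who knows that cores came from an MRI-visible lesion, or from the new device, may resolve a doubtful case differently. In a comparison of two biopsy methods, that can favour one arm.

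The plan already applies the principle to the urologists but stops short of the person who grades the tissue. The coordinator, who follows in the chain, is unmasked by the plan's own text. If that role has to apply the csPCa definition by hand, an unmasked person interprets a rule that differs by biopsy type and is not cleanly worded.

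The trial is small, so a few calls can matter to the primary test.

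**Working it through.** **Inputs (section 9.0).** Standard-biopsy csPCa rate 18.1%; absolute increase 30 points, so 48.1%; one-sided 5% level and 80% power for sizing; two-sided exact p values with Fisher's test for analysis; 31 per arm for Aim 1; 36 per arm for Aim 2; about 25% of arm A MRI-negative; 10% loss; total 80.

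**The plan's own figure.** For two proportions with pooled variance and no continuity correction, n per arm = [z(0.95)·√(2·p̄·q̄) + z(0.80)·√(p1q1 + p2q2)]² / d², with p̄ = (0.181 + 0.481)/2 = 0.331.
- First term: 1.645 × √(2 × 0.331 × 0.669) = 1.095.
- Second term: 0.842 × √(0.148 + 0.250) = 0.531.
- n = 1.626² / 0.30² ≈ 29.4, so 30 per arm, or 60 in total. The plan states 62, which is close enough.
- 72 / 0.9 = 80, which matches.

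**Expected counts.** Sections 2.0 and 5.0 set arm A mpMRI+ against arm B, while section 9.0 analyses Aim 1 by intention to treat, so both layouts are shown.
- 31 per arm: 0.481 × 31 = 14.9 and 0.181 × 31 = 5.6.
- 36 per arm: 0.481 × 36 = 17.3 and 0.181 × 36 = 6.5.
- MRI-positive against arm B: 0.75 × 36 = 27 men, 0.481 × 27 = 13.0, against 6.5 of 36.

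**Two-sided Fisher p as arm A calls are downgraded one at a time.**

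| Layout | Start | p | Result that loses significance | p | Calls changed |
|---|---|---|---|---|---|
| 27 v 36 | 13 v 7 | 0.028 | 12 v 7 | 0.051 | 1 |
| 27 v 36 | 13 v 6 | 0.012 | 10 v 6 | 0.084 | 3 |
| 31 v 31 | 15 v 6 | 0.031 | 14 v 6 | 0.056 | 1 |
| 31 v 31 | 15 v 5 | 0.013 | 12 v 5 | 0.086 | 3 |
| 36 v 36 | 17 v 7 | 0.023 | 15 v 7 | 0.072 | 2 |
| 36 v 36 | 17 v 6 | 0.011 | 14 v 6 | 0.064 | 3 |
| 40 v 40 | 19 v 7 | 0.008 | 15 v 7 | 0.078 | 4 |

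The last row assumes that all 80 men are evaluable. Rounding the arm B expectation up or down changes the answer, so both are given for the first three layouts.

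**How often the result would be that close.** This sums exact binomial probabilities, at the design rates, over all tables where changing one call (or up to two calls), in either arm and either direction, would switch significance.

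| Layout | Within one call | Within two calls |
|---|---|---|
| 31 v 31 | 24% | 45% |
| 36 v 36 | 20% | 39% |
| 27 v 36 | 25% | 48% |
| 40 v 40 | 17% | 33% |

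**If there were no true difference.** With 18.1% in both groups, upgrading two arm A men turns a non-significant result significant in about 3% of trials at 36 per arm and about 5.5% at 27 v 36.

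**The case against.** Four stronger readings are tempting, and the documents do not support them.

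- **The pathologist is told the arm.** A reader might infer this from the un-blinded label and routine handling. No sentence says that the requisition carries arm, MRI or PI-RADS information. What can be said is that no masking is described.
- **The coordinator types in the csPCa diagnosis.** The case form is in an appendix that was not available, so csPCa may be calculated there. For targeted biopsy, the entry can also be checked against the recorded Gleason score and core lengths. That the coordinator knows the arm is explicit.
- **A single regrading would decide the trial.** This holds for some counts near the design rates but not others. A result close to its threshold is fragile in any small trial, and that is not evidence of biased grading.
- **The cited trial shows enough borderline cases.** Section 3's counterpart in the background quotes overall and csPCa rates whose differences are 50.5 − 43.9 = 6.6% and 29.5 − 18.1 = 11.4%. These are all cancers not classed as significant, not cases near a cut-off. They come from another device and mixed biopsy routes, and upgrading the arm B cases would work against the new method.

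It can also be said that the clinicians with most interest in the device are already kept from the reading, that no incentive for the pathology laboratory is shown, and that three to six cores per lesion look different from a 12-core set. These points are fair. They limit the size of the concern and what masking can achieve, but they do not supply the missing safeguard.

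**Conclusion.** The gap stands as a cheap improvement that should be made, not as a demonstrated bias. The coordinator's knowledge of the arm follows directly from sections 4.0 and 5.0. The pathologist's lack of masking is inferred from silence in a trial declared un-blinded.

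At the design rates, and depending on layout, the result lies within one call of the two-sided 5% threshold in 17 to 25% of trials and within two calls in 33 to 48%. Under equal true rates, two favourable upgrades would add about 3 to 5.5 percentage points of false-positive risk, which is modest.

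These figures assume the 18.1% and 48.1% rates and the two-sided test in section 9.0. They show how sensitive the test is to changed calls, not how often calls would be changed: the documents give no rate of borderline gradings or of reader disagreement.

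**What to change.** 1. Send study specimens to the same pathologist with no arm, MRI or PI-RADS information on the requisition. Keep whatever site labelling clinical reporting needs.
2. Reconcile the csPCa wording in section 2.0, section 5.0 and the Table 2 footnote. As read, the standard-biopsy rule joins its items with a conjunction and attaches a Gleason score to a count of positive cores, and the footnote shows no Gleason number. Part of this may be a conversion fault, but a program needs one unambiguous rule for each biopsy type.
3. Derive csPCa with a program written before the data are seen, from recorded Gleason score, core lengths, PSA, gland volume, number of positive cores and laterality, instead of relying on a diagnosis entered by the coordinator.

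The cost is requisition wording, a short program and a check of the case form. No extra reader, procedure or patient is needed. Table 2 already lists Gleason score, core lengths, PSA and gland volume; positive-core count and laterality must be confirmed on the form. Masking will be partial, because core and container numbers hint at the biopsy type. The programmed derivation keeps its value even so.
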